Inflammatory reactions around the MC has been associated with imminent resolution of MC (sometimes referred to as “beginning-of-the-end” [“BOTE”] sign). The investigator (or designated evaluator) will assess the presence and overall degree of inflammatory reactions at MC lesions at Baseline (before dosing) and Weeks 2 through 12. In most cases, clinical features can differentiate between BOTE and LSR. BOTE may be associated with itch, but not pain. BOTE is usually asymptomatic, self-limited, and localized to individual MC lesions and does not require discontinuation of study treatment or additional treatment. LSR is generally more diffuse, associated with significant itch or tenderness, may necessitate discontinuation of study treatment, and may need treatment for symptomatic relief (e.g., a topical corticosteroid or topical anesthetic). For very severe LSR, systemic corticosteroids may be considered. Investigators will assess the treatment area at each scheduled visit and use their medical judgement to differentiate between BOTE and LSRs. BOTE Inflammation Score and LSR score will be recorded at each visit. BOTE should not be considered an AE. When LSRs are clinically significant at the application site, the investigator should report the condition as an AE(s).

At Baseline (at least 30 minutes after dosing) and Weeks 2 through 12, the investigators will rate LSRs on individual features including erythema, flaking/scaling, crusting, swelling, vesiculation/pustulation, and erosion/ulceration. At Baseline (pre-dose) and Weeks 2 through 12, the investigators will rate BOTE signs using the BOTE Inflammation Score.

The following tables describe the scoring parameters for the BOTE Inflammation Score and LSR score.

BOTE Inflammation Score

Score	Global Assessment	Description
0	No inflammation	No evidence of local inflammation
1	Mild	Minimal erythema and/or edema
2	Moderate	Definite erythema and/or edema with or without hemorrhagic crusting
3	Severe	Erythema and edema with definite hemorrhagic crusting
4	Very severe	Strong reaction spreading beyond the treated area, bullous reaction, erosions

LSR Score

Score	Erythema	Flaking/ Scaling	Crusting	Swelling	Vesiculation/ Pustulation	Erosion/ Ulceration
0	Not present	Not present	Not present	Not present	Not present	Not present
1	Slightly pink	Mild, limited	Isolated crusting	Minimal, limited	Fine vesicles	Superficial erosion

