12. OTHER ANALYSES

The following analyses of BOTE vs lesion count/complete clearance will be presented:

- Percent change from Baseline at Week 12 in relation to the highest BOTE score during treatment.
- Complete clearance at Week 12 in relation to the highest BOTE score during treatment.

- Percent change from Baseline at each visit in relation to BOTE score at Week 2.
- Complete clearance at each visit in relation to BOTE score at Week 2.

In these analyses, the BOTE scores will be analyzed in the ITT Population as follows:

1. Dichotomized:

- a. Score of 0 or 1: No to Mild
- b. Score of 2, 3, or 4: Moderate to Very Severe

A shift table comparing the baseline BOTE score to each scheduled postbaseline assessment will be presented for the Safety Population.

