13.3 Events of Special Interest

Events of Special Interest will include subjects with any TEAE where the preferred term contains “application site”, subjects with at least 1 post-baseline occurrence of moderate BOTE inflammation score, or subjects with at least 1 post-baseline LSR component score ≥ 1 . A summary including the number and percentage of subjects with at least 1 event of special interest, AEs of interest by MedDRA system organ class and preferred term, at least 1 moderate BOTE inflammation score, and any LSR component score ≥ 1 will be provided for the Safety Population. The analysis will also be repeated with the LSR criteria revised to include any post-baseline LSR component (excluding erythema) score ≥ 1 and erythema score ≥ 2 .

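### Events of Special Interest count a 'moderate' BOTE score (score 2) only, so read literally a subject who scores 3 or 4 but never 2 is left out of the BOTE row

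*Combined protocol and SAP*

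**What the plan says.** The references are to the final SAP version, the one that points to table shells Version 3.0. The BOTE wording in section 13.3 is the same in the two earlier SAP versions.

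- **SAP 13.3, definition.** One of three ways into Events of Special Interest is "at least 1 post-baseline occurrence of moderate BOTE inflammation score". The other two are a TEAE whose preferred term contains 'application site', and "subjects with at least 1 post-baseline LSR component score" of 1 or more.
- **SAP 13.3, summary.** The Safety Population table (14.3.6.2) is to show, among other rows, subjects with "at least 1 moderate BOTE inflammation score".
- **SAP 4, BOTE scale.** Score 2, moderate: "Definite erythema and/or edema with or without hemorrhagic crusting". Score 3, severe: "Erythema and edema with definite hemorrhagic crusting". Score 4, very severe: "Strong reaction spreading beyond the treated area, bullous reaction, erosions".
- **SAP 12.** For the analyses of BOTE against lesion response, the upper category is "Score of 2, 3, or 4: Moderate to Very Severe".
- **SAP 4, status of BOTE.** "BOTE should not be considered an AE".

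**The concern.** 'Moderate' is the label of a single level on a five-level scale, and section 13.3 adds neither 'or worse' nor a threshold. Taken at its word, the rule flags a subject with a single score of 2 but not a subject who goes from 1 to 4. A row built that way does not rise steadily with severity. A subject whose reaction moves from 2 to 3 before the first post-baseline assessment drops out of it.

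Table 14.3.6.2 is the subject-level summary of these reactions. A reader would take its BOTE row as the number of subjects who were ever moderate or worse, and the literal rule does not produce that number.

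There is also a programming risk. SAP Appendix C requires independent double programming of datasets and reprogramming of tables. Two programmers could code 'equal to 2' and '2 or more', with no text to settle which is right. They could equally both code the literal rule and agree on it.

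**Working it through.** The plan states no figure to reproduce, and no sample size or power calculation is involved. The check compares the texts and then counts score patterns to show exactly who is missed.

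**1. The passages side by side**

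| Place in SAP | How the group is expressed | BOTE scores covered |
|---|---|---|
| Section 4, scale | Moderate | 2 |
| Section 12, dichotomy | Moderate to very severe, scores listed | 2, 3, 4 |
| Section 13.3, definition | Moderate, no threshold | 2 |
| Section 13.3, summary row | Moderate, no threshold | 2 |

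Section 12 lists the scores when it means the wider group. The LSR criterion, in the same sentence of 13.3 as the BOTE criterion, carries an explicit 'at least 1' threshold. The BOTE criterion carries none. The LSR wording in 13.3 was revised between SAP versions (an erythema score of 2 or more was added to the repeat analysis), while the BOTE wording was left as it was.

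**2. Who is missed**

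The rule asks for at least one occurrence over the scheduled post-baseline visits, which are Weeks 2, 4, 8 and 12. So:

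- any visit at 2, whatever the other scores: counted;
- a 3 or 4 at some visit and no 2 at any visit: not counted;
- all scores 0 or 1: not counted under either reading.

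**3. Pattern count (illustration only)**

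With five possible scores at four visits there are 5^4 = 625 score patterns.

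- Flagged by 'any score equal to 2': 625 − 4^4 = 625 − 256 = 369.
- Flagged by 'any score of 2 or more': 625 − 2^4 = 625 − 16 = 609.
- Difference: 609 − 369 = 240. All of these contain a 3 or 4 and none contains a 2.
- Patterns with any 3 or 4: 625 − 3^4 = 625 − 81 = 544. The literal rule misses 240 of them and keeps 544 − 240 = 304, which also contain a 2.

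These are counts of possible patterns, not expected frequencies of subjects. They show that the literal rule misses some subjects with severe scores and keeps others. They say nothing about how many subjects will be affected.

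**4. Other routes into the overall count**

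A missed subject can still enter through an LSR component score of 1 or more or an application-site TEAE. Neither is automatic. BOTE is not recorded as an AE, and SAP section 4 asks investigators to separate BOTE from LSR by judgement. Where one of these routes does apply, it corrects the overall count and leaves the BOTE row as it was.

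**The case against.** The case on the other side has four parts.

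- **The scores are reported elsewhere.** Section 12 provides a Safety Population shift table from baseline BOTE to each post-baseline assessment. Table 14.2.3.10.5 gives BOTE results by visit in the same population, and Listing 16.2.9.1 gives every score by subject. This stands: no severe score disappears from the report. But the two tables work visit by visit, and the listing is not a count. Table 14.2.3.10.1 does use the highest dichotomized score, but it is an ITT display of lesion counts. None of them gives the number of Safety Population subjects who were ever moderate or worse.
- **The LSR threshold is very low.** A component score of 1 can be skin that is slightly pink, and a reaction that scores 3 or 4 on BOTE would often score at least that. This largely protects the overall count, though not with certainty, and it does not repair the BOTE row.
- **BOTE is not the main safety signal.** Protocol 7.2.3 treats it as part of normal disease progression, and the list of safety assessments in SAP section 4 omits it. Against that, protocol 3.4 lists the BOTE score among the safety assessments, and SAP 13.3 chose to give it a row.
- **The intent can be inferred.** The grouping in section 12 points to a threshold of 2 or more, and the unseen shells may already say so. That is a reason to rate the point as minor; the SAP text still needs correcting.

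A reader might infer two stronger things. One is that every subject with a severe or very severe score is left out. The rule does not do that, since one visit at score 2 is enough to be counted. The other is that the omission is largest in whichever arm reacts more. The documents do not support this. The number missed depends on how often a 3 or 4 occurs without any 2, a more reactive arm may also record more 2s, and no distribution by arm is given.

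**Conclusion.** The point holds as a minor defect of definition. As written, the BOTE row counts subjects with at least one post-baseline score equal to 2. It omits those with a 3 or 4 who never score 2.

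The number of subjects affected, and any difference between arms, cannot be derived from the documents. The consequence is limited to the descriptive Events of Special Interest summary; efficacy inference, alpha and power are unaffected.

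The conclusion rests on two assumptions: that 'moderate' in 13.3 carries the meaning it has in the SAP's scale, and that the table shells, which were not available, do not already define the row as 2 or more.

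**What to change.** In both places in SAP 13.3, the definition and the summary row, write: at least 1 post-baseline BOTE inflammation score of moderate or worse (score of 2 or more). This matches the grouping in section 12. Check that the row label in the shell for Table 14.3.6.2 agrees. If score 2 alone really is intended, say so and give the reason.

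The cost is a few words of SAP text and, if needed, one row label. All BOTE scores are already collected, so no data collection or design change is involved.

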13.4 Urine Pregnancy Test

Urine pregnancy test results will be included in a data listing only.

13.5 Physical Examination

A shift table summarizing the shift from Baseline to end of treatment in normal/abnormal will be presented.

13.6 Patch Testing

A table summarizing any patch testing results by time point may be presented.

14. CHANGES TO PROTOCOL-SPECIFIED ANALYSES

The following modifications and/or clarifications to the methodology specified in the protocol will be:

- The DLQI and CDLQI will be summarized separately
- The order of the exploratory endpoints was updated
- The Mean percent change in baseline endpoint was updated to be more generic in order to analyze the median in the case of skewness
- Proportion of subjects with 90% and 95% clearance exploratory endpoints were added in order to provide additional clinically meaningful categories for analysis

16. APPENDICES

Appendix A: Dermatology Life Quality Index (DLQI) and Children's Dermatology Life Quality Index (CDLQI) Scoring

DLQI:

Question	Scoring	Subscale
1. Over the last week, how itchy, sore, painful or stinging has your skin been?	Very much = 3 A lot = 2 A little = 1 Not at all = 0	Symptoms and Feelings
2. Over the last week, how embarrassed or self conscious have you been because of your skin?	Very much = 3 A lot = 2 A little = 1 Not at all = 0	Symptoms and Feelings
3. Over the last week, how has your skin interfered with you going shopping or looking after your home or garden ?	Very much = 3 A lot = 2 A little = 1 Not at all/Not Relevant = 0	Daily Activities
4. Over the last week, how much has your skin influenced the clothes you wear?	Very much = 3 A lot = 2 A little = 1 Not at all/Not Relevant = 0	Daily Activities
5. Over the last week, how much has your skin affected any social or leisure activities?	Very much = 3 A lot = 2 A little = 1 Not at all/Not Relevant = 0	Leisure
6. Over the last week, how much has your skin made it difficult for you to do any sport ?	Very much = 3 A lot = 2 A little = 1 Not at all/Not Relevant = 0	Leisure
7. Over the last week, has your skin prevented you from working or studying ? If "No", over the last week how much has your skin been a problem at work or studying ?	Yes = 3 No Not Relevant = 0 A lot = 2 A little = 1 Not at all = 0	Work and School
8. Over the last week, how much has your skin created problems with your partner or any of your close friends or relatives ?	Very much = 3 A lot = 2 A little = 1 Not at all/Not Relevant = 0	Personal Relationships

Question	Scoring	Subscale
9. Over the last week, how much has your skin caused any sexual difficulties ?	Very much = 3 A lot = 2 A little = 1 Not at all/Not Relevant = 0	Personal Relationships
10. Over the last week, how much of a problem has the treatment for your skin been, for example by making your home messy, or by taking up time?	Very much = 3 A lot = 2 A little = 1 Not at all/Not Relevant = 0	Treatment

Note: DLQI is administered in subjects \geq 16 years old.

The DLQI composite score is then the sum of the scores to all 10 questions and will range from 0 to 30. If 1 question is unanswered, this is allocated a score of 0 and the DLQI score is then summed. If 2 or more questions are unanswered, the questionnaire is not scored.

The subscales will be expressed as percentages of the maximum score:

Subscale	Maximum Score
Symptoms and Feelings	6
Daily Activities	6
Leisure	6
Work and School	3
Personal Relationships	6
Treatment	3

CDLQI:

Question	Scoring	Subscale
1. Over the last week, how itchy , “scratchy” , sore , or painful has your skin been?	Very much = 3 Quite a lot = 2 Only a little = 1 Not at all = 0	Symptoms and Feelings
2. Over the last week, how embarrassed or self conscious , upset or sad have you been because of your skin?	Very much = 3 Quite a lot = 2 Only a little = 1 Not at all = 0	Symptoms and Feelings
3. Over the last week, how has your skin affected your friendships ?	Very much = 3 Quite a lot = 2 Only a little = 1 Not at all = 0	Personal Relationships
4. Over the last week, how much have you changed or worn different or special clothes/shoes because of your skin?	Very much = 3 Quite a lot = 2 Only a little = 1 Not at all = 0	Leisure
5. Over the last week, how much has your skin trouble affected going out , playing , or doing hobbies ?	Very much = 3 Quite a lot = 2 Only a little = 1 Not at all = 0	Leisure
6. Over the last week, how much have you avoided swimming or other sports because of your skin trouble?	Very much = 3 Quite a lot = 2 Only a little = 1 Not at all = 0	Leisure
7. Last week , was it school time ? If school time : Over the last week, how much did your skin problem affect your school work ? Was it holiday time ? If holiday time : Over the last week, has your skin problem interfered with your enjoyment of the holiday ?	Prevented school = 3 Very much = 3 Quite a lot = 2 Only a little = 1 Not at all = 0	School or Holidays
8. Over the last week, how much trouble have you had because of your skin with other people calling you names , teasing , bullying , asking questions or avoiding you ?	Very much = 3 Quite a lot = 2 Only a little = 1 Not at all = 0	Personal Relationships

Question	Scoring	Subscale
9. Over the last week, how much has your sleep been affected by your skin problem?	Very much = 3 Quite a lot = 2 Only a little = 1 Not at all = 0	Sleep
10. Over the last week, how much of a problem has the treatment for your skin been?	Very much = 3 Quite a lot = 2 Only a little = 1 Not at all = 0	Treatment

Note: CDLQI is administered in subjects 4 years old up to 16 years old.

The CDLQI composite score is then the sum of the scores to all 10 questions and will range from 0 to 30. If a question is unanswered, this is allocated a score of 0 and the CDLQI score is then summed.

The subscales will be expressed as percentages of the maximum score:

Subscale	Maximum Score
Symptoms and Feelings	6
Leisure	9
School or Holidays	3
Personal Relationships	6
Sleep	3
Treatment	3

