10.1 Efficacy Endpoints

The primary efficacy endpoint is the proportion of subjects with complete clearance of all treatable MC at Week 12.

The secondary efficacy endpoint is the proportion of subjects with complete clearance of all treatable MC at Week 8.

Complete clearance is defined as having a total number of lesions count of 0.

The exploratory endpoints are the following:

- Proportion of subjects with complete clearance of all treatable MC at Week 2 and Week 4 visits
- Proportion of subjects achieving at least a 95% reduction from Baseline in the number of all treatable MC at each visit (Weeks 2, 4, 8, 12)
- Proportion of subjects achieving at least a 90% reduction from Baseline in the number of all treatable MC at each visit (Weeks 2, 4, 8, 12)
- Proportion of subjects achieving at least a 75% reduction from Baseline in the number of all treatable MC at each visit (Weeks 2, 4, 8, 12)
- Percent change from Baseline in number of treatable MC at each visit (Weeks 2, 4, 8, 12)
- Change from Baseline in number of treatable MC at each visit (Weeks 2, 4, 8, 12)
- Proportion of subjects who have a recurrence of MC after the first visit at which complete clearance was observed, defined as the total lesion count being greater than 0 at any point after achieving a count of 0

- Time to complete clearance of all treatable MC, defined as the days between the date of first dose and the first date of clearance. Subjects who do not achieve complete clearance will be censored at the date of the last lesion count assessment.
- Proportion of subjects with scarring, defined as an answer of Yes to either question on the Scarring/Keloid Assessment eCRF page: “Was the presence of a scar > 1 mm deep and/or 5 mm wide noted?” or “Was the presence of a scar noted?”, after clearance of lesion(s) at each visit (Weeks 4, 8, 12, 24)
- Proportion of subjects with keloid or hypertrophic scar, defined as an answer of Yes to the Scarring/Keloid Assessment eCRF page question “Was the presence of a keloid or hypertrophic scar noted?”, after clearance of lesion(s) at each visit (Weeks 4, 8, 12, 24)
- Change from Baseline of the composite score from age-matched (at Baseline) Dermatology Life Quality Index (DLQI) or Children’s Dermatology Life Quality Index (CLDQI) assessment at Week 12
- Subject-reported spread to household members as measured by any new occurrence of MC in household members of subjects at each visit (Weeks 2, 4, 8, 12, 16, 20, 24)

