11.3 Exploratory Analyses

The exploratory endpoints based on the proportion of subjects achieving complete clearance or 75%, 90%, or 95% reductions will be analyzed in the same manner as the primary endpoint.

Since the within-household correlation is expected to be small and the change and percent change from Baseline in the number of treatable MC are exploratory, they will be analyzed using a repeated measures mixed model for the respective visits with the same covariates as the primary model together with visits and treatment by visit; an unstructured covariance matrix will be utilized. If the calculation of the percent change from baseline is influenced by outliers with calculated values >100%, then the influence of outliers will be avoided for analysis by censoring them so that all values were in the range of -100% to 100%. If the model fails to converge, then other correlation structures will be explored.

Since the within-household correlation is expected to be small and time to first complete clearance of all MC is exploratory, it will be analyzed using Kaplan-Meier methods. The number and percentage of subjects achieving complete clearance, number and percentage of censored subjects, and Kaplan-Meier estimates of first quartile, median, and third quartile will be summarized by treatment group. Differences in Kaplan-Meier curves between the treatments will be tested for significance using a stratified log-rank test.

The proportion of subjects with scarring and the proportion of subjects with keloid or hypertrophic scarring will be summarized descriptively at each visit.

The change from Baseline of the composite score from age-matched (at Baseline) DLQI/CDLQI will be summarized descriptively and separately for each questionnaire. The scoring algorithms are detailed in [Appendix A](#). The CDLQI will be examined in the following Week 12 response categories: complete clearance, 95% reduction in lesion counts, 90% reduction in lesion counts, and subjects who did not achieve complete clearance. Additionally, the changes from Baseline in the following subscales: Symptoms and Feelings, Daily Activities, Leisure, Work and School, Personal Relationships, and Treatment, for DLQI, and Symptoms and Feelings, Leisure, School or Holidays, Personal Relationships, Sleep, and Treatment, for CDLQI, and each question will be summarized descriptively.

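### The CDLQI scoring rule counts an unanswered question as 0 and sets no limit on blanks, unlike the DLQI rule in the same appendix

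*Combined protocol and SAP*

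**What the plan says.** Protocol 7.1.2 assigns the DLQI to subjects aged 16 and over and the CDLQI to those from 4 up to 16. It says only that each score is a sum running from 0 to 30. Both forms are given at Baseline and at Week 12/ET1 (protocol Table 1).

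SAP Appendix A then sets out the scoring, with different rules for unanswered questions:

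- DLQI: "If 1 question is unanswered, this is allocated a score of 0 and the DLQI score is then summed". And: "If 2 or more questions are unanswered, the questionnaire is not scored".
- CDLQI: "The CDLQI composite score is then the sum of the scores to all 10 questions and will range from 0 to 30". And: "If a question is unanswered, this is allocated a score of 0 and the CDLQI score is then summed". Nothing further is said about blanks.

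The usual CDLQI response scale is "Very much = 3 Quite a lot = 2 Only a little = 1 Not at all = 0", so 0 is the lowest impairment.

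The score feeds one exploratory endpoint in SAP 10.1, taken at Week 12: "Change from Baseline of the composite score from age-matched (at Baseline) Dermatology Life Quality Index (DLQI) or Children’s Dermatology Life Quality Index (CLDQI) assessment". SAP 11.3 says that it "will be summarized descriptively and separately for each questionnaire". SAP 11.3 also asks for subscale changes, individual questions, and CDLQI summaries by Week 12 lesion response (Tables 14.2.3.8.3.2 to 14.2.3.8.3.5).

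No other section supplies a limit. SAP 10.4 deals with response endpoints and counts a missing response as a non-response. SAP Section 14 records that the two questionnaires are summarised separately, but does not explain the different rules.

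**The concern.** Giving a skipped question the best possible answer always lowers the recorded score or leaves it unchanged. With one blank out of ten the distortion is small, and the SAP accepts it for both questionnaires. With several blanks it can be large. For adults the SAP guards against this by declining to score the form; for children it states no such guard.

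The CDLQI is the form most subjects of scorable age are likely to complete, since the protocol describes MC as mainly a disease of children. Its questions as listed in Appendix A carry no not-relevant option, whereas eight of the ten DLQI questions do, so a child to whom a question does not apply may leave it blank.

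What is at stake is the quality-of-life description: the composite change, the subscales, and the tables that set CDLQI change beside lesion response.

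**Working it through.** **Inputs.** There are ten questions, each scored 0 to 3, a blank counts as 0, and the total runs from 0 to 30 (SAP Appendix A). Change is the post-baseline value minus the baseline value (SAP Appendix B). The true item values below are assumptions, because the documents give no item-level data.

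**The plan's own figure.** 10 × 3 = 30, and the CDLQI subscale maxima give 6 + 9 + 3 + 6 + 3 + 3 = 30. The stated range is reproduced.

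**Ceiling with m blanks.** Only 10 − m questions can contribute, so the highest attainable total is 3 × (10 − m).

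**Recorded total with m blanks.** If every item truly has value a, the true total is 10a, the recorded total is a × (10 − m), and the understatement is a × m.

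| Blanks m | Ceiling | Recorded if a = 1 (true 10) | Recorded if a = 2 (true 20) | Recorded if a = 3 (true 30) | DLQI rule for the same blanks |
|---|---|---|---|---|---|
| 1 | 27 | 9 | 18 | 27 | scored |
| 2 | 24 | 8 | 16 | 24 | not scored |
| 5 | 15 | 5 | 10 | 15 | not scored |

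**Effect on change from baseline.** Take a child with no true change.

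- Complete baseline, five blanks at Week 12, a = 1: recorded change 5 − 10 = −5, a false improvement of 5 points. For a = 2 and a = 3 it is 10 − 20 = −10 and 15 − 30 = −15.
- Five blanks at baseline, complete Week 12, a = 1: recorded change 10 − 5 = +5, a false worsening.

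When items differ in value, the loss from m blanks lies between 0 and 3m, depending on which questions are skipped. The equal-item case is an illustration, not an estimate.

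**Wholly blank form.** Arithmetically m = 10 gives 0, but only if the form is entered as completed. The SAP does not say whether it would be.

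**Subscales.** School or Holidays, Sleep and Treatment each rest on one question with a maximum of 3. If a blank is carried into the subscale as 0, the result is 0/3 = 0%, whatever the truth. The DLQI has the same exposure in its one-question subscales (Work and School, Treatment), and the SAP states no separate subscale rule for either form.

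**The other reading of the sentence.** The CDLQI rule speaks of one question in the singular. If it is taken to cover exactly one blank, nothing in the SAP covers two or more. Appendix C requires two independently programmed datasets to match, so a difference in reading would surface, but the SAP would not settle it.

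**The case against.** The strongest reply has four parts.

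1. *The absence of a cap is not an instruction to score any number of blanks.* The sentence is singular, so a reader who infers that every blank must be set to 0 goes further than the words. This stands as a limit on the claim, but the alternative reading leaves a gap where a rule is needed.

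2. *A blank form may never be scored.* A reader might infer that an empty questionnaire is recorded as no impairment and so as the largest possible improvement. The documents do not establish this. SAP Section 6 counts non-missing values and bases by-visit denominators on non-missing data, so an empty form could well be treated as not done. Nor does a half-blank form necessarily show little impairment: five answered questions can still total 15. It is understated, not necessarily low.

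3. *The consequence is small.* The endpoint is exploratory and descriptive, with no planned test. The same rule applies to both arms of a double-blind trial, and blanks at baseline and at Week 12 push the change in opposite directions. A reader might infer a bias in favour of SB206, but nothing in the documents shows a difference between arms or a net direction. This stands, and it sets the severity.

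4. *The two instruments may have different scoring instructions.* The SAP cites a separate source for each, and those sources cannot be consulted here. That is a reason to check them when making the change. It does not supply the missing explanation, since neither Appendix A nor Section 14 says that the difference is deliberate.

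**Conclusion.** The point holds, and it is minor. Appendix A scores a blank CDLQI question as the best answer and states no limit, while the DLQI beside it stops being scored at two blanks. Taken as written, the CDLQI ceiling falls to 24 with two blanks and 15 with five. Under the stated assumption of equal item values of 1, 2 or 3, five blanks at one visit shift an individual's change by 5, 10 or 15 points.

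The effect reaches the CDLQI composite, its subscales and the CDLQI tables by Week 12 response, and nothing else. Its size in a group mean cannot be computed, because the documents give no expected rate of incomplete forms.

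**What to change.** In SAP Appendix A, replace the CDLQI sentence on blanks with the limit that the SAP already uses for the DLQI: one unanswered question scores 0; with two or more unanswered, the questionnaire is not scored. This also settles the wholly blank form and removes the ambiguity of the singular wording. If the sponsor keeps a different rule because the cited CDLQI instructions require it, Appendix A should say so and state what happens with two or more blanks.

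The change costs one sentence and one line of derivation, made before the Week 12 data are unblinded. The price is that CDLQI forms with two or more blanks become missing; how many cannot be said from the documents.

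A rule for a subscale with a missing item is a separate, optional choice. It is not part of the DLQI limit, and if one is added it should be the same for both questionnaires.
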